Using 152 MSM iTAB subjects categorized into perfect (37), high (n=85) and moderate (n=40). Those found 37 (24%) reporting perfect adherence in the past 34 days (representing two TFV-DP half lives) with mean TFV-DP concentrations of 1457 fmol/punch +/-694 fmol/punch. This corresponds almost exactly with predicted DBS concentrations for drug exposure of 7 doses per week in controlled pharmacokinetic studies where perfect adherence was associated with a level of 1460 fmol/punch (39). These data can therefore be used as the comparison to data derived in transgender women on csHT with perfect adherence by iTAB.

Sub-study IV Background and Significance

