At Weeks 0, 12, and 48, applicable subjects will complete the Body Image Scale (mBIS) questionnaire, and answer questions about general hormone therapy satisfaction.

SUB-STUDY STATISTICAL CONSIDERATIONS

Sample Size and Power

The primary aim of this analysis is to determine if PrEP interacts with hormone therapy in either direction that would impact either i) efficacy of PrEP to reduce HIV acquisition or ii) hormones to achieve desirable gender traits. Of our 300 person cohort, we estimate that 280 individuals will be MAAB Of those 280 MAAB, we predict that 70% will be taking feminizing hormones (n=196) and 30% will be on no hormonal therapy (n=84), based on previous population estimates (97). Based on adherence results in individuals randomized to iTAB (98), we estimate that 25% of participants will have perfect adherence to PrEP.

[figure not shown]

Figure 2: Predicted Numbers of Individuals on HRT and PrEP

Statistical power is based on a one-sample non-inferiority test to see if the TFV-DP concentration of perfectly adhered MAAB persons is equivalent to MSMs on average under an acceptable margin. The following assumptions are made: i) Using PK modeling of HIV-uninfected men and women, it has been shown that perfect adherers (i.e. daily dosing for 7 days) have TFV-DP concentrations of 1560 (IQR 1246-2029) fmol/punch as determined in MSM; ii) Since this is a non-inferiority study, we will assume the expected sample mean for MAAB is around 1560 fmol/punch, or slightly lower. In other words, we will assume the mean difference in TFV-DP concentrations between MAAB and MSMs is approximately 0 (ranges from -180 to 50); and iii) We believe that a difference of less than 230 fmol/punch (equivalent to 1 tablet per week dosing) in the TFV-DP concentration can be considered non-inferiority which will be the lower limit of acceptable variation. Thus, we will set the non-inferiority margin to be 230.

Assuming the standard deviation is 350, if the true mean TFV-DP concentration for MAAB is 1360 fmol/punch (ie, 100 fmol/punch lower than MSMs), then 45 subjects are required to be 80% confident that the lower limit of a one-sided 95% confidence interval of the mean difference between MAAB and MSMs will be above the non-inferiority limit of -230.

Analysis Plan

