10. HUMAN SUBJECTS

The study will enroll about 300 self-identified transgender or gender-nonconforming individuals ages 18 and older at all participating sites. UCSD and FHCSD plans to enroll up to 100 subjects.

Main Study Inclusion Criteria

- 1. Transgender identity, defined as identifying differently from sex assigned at birth.
- 2. Age 18 years or older.
- 3. Risk of acquisition of HIV as evident by one or more of the following:
 - I. Has at least one HIV infected sexual partner for ≥4 weeks.

OR

II. Anticipated or concern of unprotected anal or vagina sex with a partner in the next 3 months

OR

- III. Any partner in the past 12 months AND at least one of the following:
 - a. any condomless anal or vaginal sex in the past 12 months;
 - b. any STI diagnosed or reported in the past 12 months;
 - c. exchange of money, gifts, shelter, or drugs for sex;

OR

- IV. Post Exposure Prophylaxis (PEP) use in the past 12 months.
- 4. Negative for HIV infection by nucleic acid test (NAT) or other sensitive method such as 4th generation antibody- antigen test.
- 5. Acceptable renal function as measured by calculated creatinine clearance of at least 60 mL/min by the Cockcroft-Gault formula (eCcr (male) in mL/min = [(140 age in years) x (lean body weight in kg)] / (72 x serum creatinine in mg/dL) in the past 30 days.

Main Study Exclusion Criteria

- 1. Unable to give informed consent.
- 2. Active hepatitis B defined by a positive hepatitis B surface antigen (HBSAq)
- 3. Substantial medical condition, that in the opinion of the investigator would preclude participation, as defined by
 - gastrointestinal condition that would impair absorption of study drugs.
 - Known condition of reduce bone density (e.g. osteoporosis or osteogenesis imperfect) that significantly elevate the risk of bone fracture
 - Neurological or severe psychiatric condition that would significantly impair the ability to adhere to PrEP.
 - Tubular or glomerular kidney disease that could be exacerbated by tenofovir
 - Other medical condition that would unacceptably increase the risk of harm from study drug or significantly impair the ability to adhere to PrEP.
- 4. Suspected sensitivity or allergy to the study drug or any of its components.
- 5. Currently using an essential product or medication that interacts with the study drug such as the following:
 - Other antiretroviral agent (including nucleoside analogs, non-nucleoside reverse transcriptase inhibitors,

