integrase inhibitors, protease inhibitors or investigational antiretroviral agents) – if currently on TDF/FTC for PEP or PrEP they can switch to study provided drug but can not continue any other antiretroviral agent.

- Agents with known nephrotoxic potential:
 - aminoglycoside antibiotics (including gentamicin)
 - IV amphotericin B
 - cidofovir
 - o cisplatin
 - foscarnet
 - IV pentamidine
 - IV vancomycin
 - o oral or IV gancyclovir
 - other agents with significant nephrotoxic potential
- Drugs that slow renal excretion
 - Probenecid
- Immune system modulators
 - Systemic chemotherapeutic agents (i.e. cancer treatment medications)
 - Ongoing systemic corticosteroids (with the exception of short courses of tapering steroid doses for asthma or other self- limited condition).
 - Interleukin-2 (IL-2)
 - Interferon (alpha, beta, or gamma)
- Other agent known to have a significant interaction with TDF or FTC
- 6. Proteinuria 2+ or greater by urine dipstick
- 7. Pregnancy (if individual has a uterus)
- 8. Other condition that in the opinion of the investigator would put the participant at risk or interfere with participation, complicate interpretation of study outcome data, or otherwise interfere with achieving the study objectives.

Participation into Sub-study IV will be only be offered to a subset of 20 transgender men/gender non-conforming individuals with vaginas enrolled at the UCSD AVRC. Transgender women enrolled at the UCSD AVRC who have undergone gender reassignment surgery with neovaginas will also be offered participation, although we expect this number to be guite low.

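### Sub-study IV's stated size and power (20 people at one clinic, n=40 in the power statement) are hard to reconcile with the plan's own estimate of about 20 non-MAAB participants over five sites

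*Combined protocol and SAP*

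**What the plan says.** **Sub-study I** (Section 9, Sub-study Statistical Considerations, Sample Size and Power) starts from the sex-at-birth projection: "Of our 300 person cohort, we estimate that 280 individuals will be MAAB". It then assumes that "70% will be taking feminizing hormones (n=196) and 30% will be on no hormonal therapy (n=84"), and adds: "we estimate that 25% of participants will have perfect adherence to PrEP". The requirement set against this is that "45 subjects are required to be 80% confident that the lower limit of a one-sided 95% confidence interval" clears the margin of 230 fmol/punch.

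**Sub-study IV** (end of Section 10) is "offered to a subset of 20 transgender men/gender non-conforming individuals with vaginas enrolled at the UCSD AVRC". Transgender women with neovaginas at the same clinic may also join, but the plan expects very few. The power statement (Section 9, Sub-study IV Statistical Considerations, Aim 1) takes a mean of 119 and an SD of 58 ng/mL and claims 80% power at one-sided alpha 0.05 to detect a 33 ng/mL (28%) reduction with n=40. The planned analysis compares participants with any vaginal infection against those with none.

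**Sites.** Section 7 (Study Rationale) names five sites. Section 10 says "UCSD and FHCSD plans to enroll up to 100 subjects"; Section 5 gives the same 100 to UCSD. No enrolment figure is given for the AVRC alone.

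**Comparator data.** Section 7 (Preliminary Data) reads "Using 152 MSM iTAB subjects categorized into perfect (37), high (n=85) and moderate (n=40").

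**The concern.** Taking 280 from 300 leaves 20 participants who are not MAAB, for all five sites together. (Intersex participants are placed in the female stratum.) Sub-study IV names the same number, 20, for a single clinic and calls them a subset, which suggests a pool there of more than 20. Its power statement uses twice that number. Nothing in the text connects the three figures.

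If the 280/20 projection is right, Sub-study IV will probably recruit well short of 20 and have little chance of detecting the difference it claims to be powered for. A null comparison of tenofovir levels by infection status could then be read as evidence of no effect. If instead the clinic does expect 20 or more, the trial may hold more female-assigned participants than Sub-study I assumed, and the pool of perfectly adherent MAAB participants on hormones shrinks.

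**Working it through.** **1. Reproduce Sub-study I.**
- Chain: 280 × 0.70 = 196 on hormones; 280 × 0.30 = 84 not; 196 × 0.25 = 49 with perfect adherence.
- Requirement: SD 350, margin 230, true difference 100, one-sided alpha 0.05, power 80%. n = [350 × (1.645 + 0.842) / (230 − 100)]² = 44.8, so 45. The plan's figure reproduces; exact one-sample t power at 45 is 79%.
- The 100 is taken as stated. The passage reads "Assuming the standard deviation is 350, if the true mean TFV-DP concentration for MAAB is 1360 fmol/punch (ie, 100 fmol/punch lower than MSMs"), although 1360 is 100 below the 1460 in Preliminary Data, not below the 1560 given as the reference in the same paragraph. That is a separate matter.

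**2. Implied non-MAAB total.** 300 − 280 = 20, or 6.7%. Twenty at the AVRC is 100% of that total, and 20% of the San Diego maximum of 100.

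**3. Expected number in San Diego.** Assume non-MAAB participants are spread in proportion to enrolment and San Diego reaches 100. The expected number is 20 × 100/300 = 6.7, with a hypergeometric 95% range of 3 to 11. This covers UCSD and FHCSD together, so the AVRC alone would have no more.

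**4. Sub-study IV power.** Two independent groups, SD 58, difference 33 (33/119 = 28%, as stated), one-sided alpha 0.05:
- Per-group n = 2 × [58 × (1.645 + 0.842) / 33]² = 38.2, so 39 per group.

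| Total n (equal groups) | Per group | Power, normal approximation | Power, t-test |
|---|---|---|---|
| 20 | 10 | 35% | 34% |
| 40 | 20 | 56% | 55% |
| 80 | 40 | 82% | 81% |

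The claimed 80% therefore fits n=40 only if it means 40 per group, 80 in all. Unequal groups lower the power: with 40 in total and 30% infected (illustrative), the t-test has 49%.

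**5. Effect on Sub-study I if there are more female-assigned participants.** With F female-assigned, the expected n is (300 − F) × 0.70 × 0.25.
- F = 20: 49
- F = 30: 47.3
- F = 40: 45.5
- F = 42: 258 × 0.175 = 45.2, still at least 45
- F = 43: 257 × 0.175 = 44.98, just below 45
- F = 60 (a 20% share at every site, an assumption): 42, exact power about 76%

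**6. Comparator counts.** 37 + 85 + 40 = 162, not 152.

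**The case against.** The strongest defence is that the figures do not strictly contradict each other. Twenty at the AVRC does not exceed 20 overall; the 280 is a planning estimate; the 20 others are obtained by subtraction and are nowhere stated; people with neovaginas can add to Sub-study IV; and the 20 can be read as a cap on offers rather than a recruitment target. All of that stands, and it is why the figures are hard to reconcile rather than incompatible. Figure 2, on predicted numbers, is also missing from the text available, so whether it projects female-assigned participants cannot be checked. The defence does not reach the n=40, which is twice the number offered participation, whatever the site distribution.

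Four stronger readings are tempting, and the documents do not support them:

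- **One of the two sub-studies must fall short of its stated number of participants.** This does not follow. With 30 to 42 female-assigned participants, 20 of them at the AVRC, Sub-study IV has its 20 and Sub-study I still expects 45 to 47.
- **Twenty in San Diego is practically impossible, and Sub-study I will have only 42.** Very small probabilities for the first, and the figure of 42, need an equal female-assigned share at every site, which the plan never states.
- **The 25% adherence rate collapses because the base is 162.** The plan prints 24% for the 37. 37/152 = 24.3% agrees and 37/162 = 22.8% does not, so an error in a category count is likelier. At 37/152, 196 gives 47.7. The 25% is also attributed to a cited reference, so its link to these counts is inferred.
- **Sub-study I cannot absorb missing dried blood spots, since 45/49 leaves 8%.** No allowance is stated, but samples are drawn at four visits and perfect adherence is defined over the past 34 days without fixing a visit, so each person has more than one chance. This is missing detail, not an error.

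**Conclusion.** The point holds for Sub-study IV. Its 20 participants at one clinic would take up the whole non-MAAB population implied for five sites, and its power statement rests on twice that number. Under the plan's own SD, difference and alpha, with equal groups, power is about 55% at 40 in total and about 34% at 20, against the stated 80%; these figures need no assumption about sites. The expectation of about 7 in San Diego does rest on proportional spread and on San Diego enrolling 100.

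For Sub-study I the consequence is conditional and modest. Its 45 reproduces and stays covered up to 42 female-assigned participants. At 60 the expected number would be 42 and power about 76%, against 79% at 45. The main trial's primary endpoint is not touched. This should be corrected, but it does not threaten the trial.

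**What to change.** - Give one projected split by sex assigned at birth and site, including an AVRC-only figure, and use it both in the Sub-study I sample-size text (Section 9) and in the Sub-study IV paragraph (Section 10).
- Reconcile 20 with 40. State whether 20 is a cap or a target, and whether n=40 is a total or per group.
- Restate Sub-study IV's expected n and power from that projection, using a realistic infected/uninfected split. If 20 or fewer are expected, label the sub-study descriptive and drop the 80% power claim.
- If more than 20 female-assigned participants are expected, restate Sub-study I's expected n as (300 − female-assigned) × 0.70 × 0.25 and set it against 45.
- Correct the comparator counts in Section 7, Preliminary Data, so that the categories sum to the stated total.

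The cost is wording in the protocol and SAP, with no added participants or procedures. Sub-study IV's stated power will look less favourable.

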The primary outcome is the intracellular TFV-DP levels, as measured in DBS, which is a continuous variable. Comparison between the MAAB and the existing MSM data that will be compared using a two-sample t-test. Differences in the means between the two groups, along with the standard deviations (SD) and their 95% confidence intervals will be reported. As a secondary/sensitivity analysis, multiple regression analysis will be performed to study the association between clinical and demographic factors (age, race, ethnicity, education, socioeconomic status, sexual risk behaviors, substance use, depression, concomitant medications) and group, adjusting for baseline demographic, stratification variables, and clinical characteristics. Variables significantly associated with both group and outcome (p<0.10) will be included in a multiple regression model as covariates.

For the main secondary hypothesis, in MAAB on csHT, to determine the change between baseline and week 12 estradiol levels in individuals taking PrEP and receiving stable estrogen replacement (controlling for route, dose and formulation), we will use a paired t-test. As estradiol concentrations can be unpredictable, we will measure estradiol concentrations in individuals choosing not to initiate PrEP at the same time points. Similar to 3A, multiple regression models will be developed if there are factors that require adjustment in this model.

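### Sub-study I is sized for 80% power with a one-sample test but analysed with a two-sample t-test, which gives about 52% power at best under the sizing assumptions; the MSM reference mean is also inconsistent

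*Combined protocol and SAP*

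**What the plan says.** The power paragraph for Sub-study I (Section 9, Sub-study Statistical Considerations, Sample Size and Power) opens: "Statistical power is based on a one-sample non-inferiority test". It gives the MSM level as 1560 fmol/punch (IQR 1246-2029) and sets a margin of 230. It expects that the mean difference "between MAAB and MSMs is approximately 0 (ranges from -180 to 50"). It then continues "Assuming the standard deviation is 350" and "if the true mean TFV-DP concentration for MAAB is 1360 fmol/punch (ie, 100 fmol/punch lower than MSMs), then 45 subjects are required" for 80% assurance that the lower one-sided 95% limit "will be above the non-inferiority limit of -230". For the number available, it predicts 196 participants assigned male at birth (MAAB) on feminizing hormones, and "we estimate that 25% of participants will have perfect adherence to PrEP".

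The Analysis Plan that follows uses a different test: "Comparison between the MAAB and the existing MSM data that will be compared using a two-sample t-test". Differences in means, "along with the standard deviations (SD) and their 95% confidence intervals will be reported".

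Section 7 gives two values for perfect adherence, both citing reference 39: 1560 in the sub-study background and 1460 under Preliminary Data. Preliminary Data also describes 37 perfectly adherent MSM with mean 1457 +/-694 and says they can serve as the comparison.

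**The concern.** A one-sample test treats the MSM mean as known. A two-sample test carries the sampling error of the MSM group as well, so a size derived for the first does not give the same power for the second. The documents point both ways. The Section 6 hypothesis, the Section 7 background and the power paragraph read as a fixed benchmark; Preliminary Data and the Analysis Plan read as two samples.

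Two further features add to the problem. No source is given for SD 350, and it is smaller than every spread the protocol quotes. The sizing sentence also cannot be reconciled with the MSM mean stated in its own paragraph.

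This is the only power statement for the sub-study's primary objective, which asks whether cross-sex hormone therapy (csHT) affects PrEP drug levels. An underpowered comparison may fail to show non-inferiority when no interaction exists, and that result could be misread as evidence of one. If the test and the reference mean are left open until data are seen, the choice could decide the conclusion.

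**Working it through.** **Inputs.** From Section 9: margin 230, one-sided 5%, SD 350, sizing deficit 100, and 196 x 0.25 = 49 perfectly adherent csHT participants. From Section 7, Preliminary Data: 37 perfectly adherent MSM, mean 1457 +/-694. From the quoted IQR, if normal: SD = (2029 - 1246)/1.349 = 783/1.349 = 580. For comparison, SD 350 implies an IQR width of 350 x 1.349 = 472.

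**1. The plan's figure.** One-sample: n = (1.645 + 0.842)^2 x 350^2 / (230 - 100)^2 = 44.8, so 45. The stated number reproduces. The same inputs in a two-sample comparison need 2 x 44.8 = 89.6, so 90 per group.

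**2. Power of the planned two-sample test, 49 vs 37.** The standard error is sqrt(SD1^2/49 + SD2^2/37). At SD 350 this is 350 x sqrt(1/49 + 1/37) = 76.2. The normal approximation at deficit 100 is Phi(130/76.2 - 1.645) = 52.4%; the noncentral t gives 51.9%. By noncentral t throughout:

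| SD (csHT / MSM) | SE | Power, deficit 100 | Power, difference 0 |
|---|---|---|---|
| 350 / 350 | 76.2 | 51.9% | 91.1% |
| 350 / 694 | 124.6 | 26.9% | 57.0% |
| 580 / 580 | 126.3 | 26.6% | 56.4% |
| 694 / 694 | 151.2 | 21.4% | 44.6% |

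Simulation with equal SDs (200,000 runs) agrees within 0.3 points.

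**3. Power if the one-sample test is kept, n = 49.**

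| SD | n for 80%, deficit 100 | Power, deficit 100 | Power, difference 0 |
|---|---|---|---|
| 350 | 45 | 82% | over 99% |
| 580 | 123.1, so about 123 | 46% | 86% |
| 694 | 176.2, so about 176 | 36% | 74% |

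With 49 participants, 80% at deficit 100 holds only while the SD is about 361 or less.

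**4. Does the result depend on 49?** If 15% to 50% are perfectly adherent (29 to 98 participants), two-sample power at deficit 100 is 43% to 61% at SD 350 and 18% to 25% at SD 694. However many csHT participants are added, 37 comparators cap it: at SD 350, Phi(130/(350/sqrt(37)) - 1.645) = 73%. The caps at SD 580 and 694 are 39% and 31%.

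**5. The reference mean.** 1560 - 1360 = 200, not 100. That lies outside the stated range of -180 to 50 and only 30 inside the margin; a true deficit of 200 would need 842 participants even in a one-sample test. The choice of reference also matters. The MSM's own mean of 1457 is 103 below 1560 but 3 below 1460. If csHT participants truly match 1457, one-sample power with 49 at SD 350, 580 and 694 is 80%, 45% and 35% against 1560. Against 1460 it is over 99%, 85% and 73%.

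**The case against.** The 45 is correct for the test the power paragraph names, and it does not drive enrolment: the sub-study uses whoever among the 300 qualifies. The plan expects a difference near 0, with a deficit of 100 as a cautious case. At SD 350, two-sample power with 49 vs 37 is 91% at 0, about 85% at -25 and about 76% at -50. The 1360 may be a slip for 1460, which would be 100 below 1560 and leave the 45 unchanged.

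Several inputs are inferred. The +/-694 is not labelled as an SD. The quoted IQR is asymmetric about 1560 (314 below, 469 above), so 580 is approximate. The Analysis Plan does not say the comparator is limited to the 37. The 49 is derived, and the figure with predicted numbers is not available. Section 9 also defers detail to a later SAP that takes precedence.

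Most of this stands as qualification, and it makes the lower end of the range less certain than the upper end. It does not remove the defect. The 52% uses the plan's own SD and deficit, and with 37 comparators no number of csHT participants lifts it above 73%. Even the narrower half of the IQR implies an SD of 314/0.6745 = 466, well above 350. The slip may run the other way, with 1460 as the MSM mean; the documents do not settle it. The objection does succeed on the decision rule: the power paragraph already gives the -230 limit, so its absence from the Analysis Plan is missing detail, not an error.

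**Conclusion.** The concern holds. The stated 80% belongs to a test the Analysis Plan does not use. Under the planned two-sample test with 49 vs 37, power at the sizing deficit of 100 is about 52% at SD 350, 27% at SD 580 and 21% at SD 694. If csHT participants truly match MSM, it is 91%, 56% and 45%. Reverting to the one-sample test restores 80% only if the SD is close to 350, which no spread in the protocol supports. Separately, and under either test, the 1360, 1460 and 1560 values are inconsistent.

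These figures assume 49 csHT participants with no loss to dropout or missing samples, 37 comparators, one value per person, +/-694 read as an SD, and the one-sided 5% level of the power paragraph. If the lower limit of a two-sided 95% interval decided instead, power at deficit 100 would be about 39% (SD 350) or 13% (SD 694).

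**What to change.** 1. **Reference mean.** State one sourced MSM mean in the Section 7 background, Preliminary Data and the power paragraph, and correct the sentence that places 1360 at 100 below MSM.

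2. **One test for sizing and analysis.**
   - *Two-sample test kept:* replace the 45-for-80% statement with: Assuming 49 perfectly adherent MAAB on csHT (196 x 25%), 37 perfectly adherent MSM and a common SD between 350 and 694, power (margin 230, one-sided 5%) is about 52% to 21% at a true difference of -100 and 91% to 45% at 0. Update the 37 if more comparators exist.
   - *One-sample test kept:* change the Analysis Plan to a one-sample comparison with the stated reference, and write: With 49 participants and SD 350 to 694, power is about 82% to 36% at -100 and over 99% to 74% at 0.

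3. **SD.** Give the source of 350, or use a value consistent with the protocol's own spreads (about 580 to 694), and say whether +/-694 is an SD.

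4. **Optional, for clarity.** Repeat in the Analysis Plan that non-inferiority is concluded only if the lower one-sided 95% bound for the mean difference (csHT participants minus MSM) exceeds -230.

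The cost is wording and a less favourable power statement. No participants or samples are added.

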Hypothesis: Among transgender MAAB persons on csHT who report perfect adherence by iTAB in the past 34 days (ie, two intracellular half-lives) the mean intracellular tenofovir-diphosphate (TFV-DP) concentrations, as measured in DBS, will be equivalent to the levels of perfect adherence previously defined in MSM.

Sub-study I Secondary Objectives

- 1. To determine whether csHT interacts with PrEP in MAAB persons that would affect hormone effectiveness, measured by estrogen concentrations assessed at Weeks 0 and 12 of study follow-up.
 - **Hypothesis**: Among transgender MAAB persons on csHT, estrogen concentrations will not change significantly between baseline (Week 0) and Week 12 in individuals taking PrEP and receiving stable estrogen therapy (controlling for route and formulation).
- 2. To determine TFV-DP in MAAB of all adherence levels compared to not taking csHT, adjusting for confounding factors.
- 3. To determine TFV-DP in MAAB taking versus not taking antiandrogen medications (i.e., spironolactone, finasteride)
- 4. To measure the change in testosterone concentrations between baseline and Week 12 in female-assigned at birth (FAAB) taking PrEP and receiving stable testosterone therapy.
- 5. To determine emtricitabine-triphosphate (FTC-TP) concentrations (a measure of recent adherence) in TG / GNC persons of all adherence levels taking versus not taking hormones.
- 6. To determine changes in desired effects of csHT in TG / GNC persons taking PrEP as measured by the Body Image Scale (BIS).

Sub-study IV Objectives:

- 1. To determine the impact of genital STIs on CVF TFV levels.
- 2. To determine the impact of cytokine mediators of CV inflammation on CVF TFV levels.
- 3. To determine the impact of CV microbiome on CVF TFV levels.

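### Sub-study I: the Analysis Plan names a two-sample t-test but does not carry over the 230 fmol/punch non-inferiority rule, so a non-significant difference could stand in for non-inferiority

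*Combined protocol and SAP*

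**What the plan says.** Three places in the combined protocol and SAP describe the Sub-study I primary question, in different statistical terms.

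- **Section 6, Sub-study I hypothesis.** Mean TFV-DP in perfectly adherent transgender MAAB participants on csHT "will be equivalent to the levels of perfect adherence previously defined in MSM".
- **Section 9, Sub-study Statistical Considerations, Sample Size and Power.** "Statistical power is based on a one-sample non-inferiority test". On the margin: "Thus, we will set the non-inferiority margin to be 230". The success condition behind the sample size concerns the lower bound of the interval: "one-sided 95% confidence interval of the mean difference between MAAB and MSMs will be above the non-inferiority limit of -230". The inputs are an SD of 350, a true mean "100 fmol/punch lower than MSMs", and 80% assurance, giving 45 subjects.
- **Section 9, Analysis Plan for the sub-study.** "Comparison between the MAAB and the existing MSM data that will be compared using a two-sample t-test". Differences in means, SDs and 95% confidence intervals are to be reported. The paragraph names no margin, shifted null, one-sided bound or criterion for success.

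The comparator is described in Section 7, Preliminary Data: 37 MSM with perfect adherence by iTAB, mean 1457 fmol/punch, +/-694.

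**The concern.** Read without further specification, a two-sample t-test has a null of zero difference. Failing to reject that null does not show that the means are close, and a smaller or noisier sample makes failure more likely. A non-inferiority test works the other way: its null is a deficit of 230 or more, and imprecision counts against the claim. Because the Analysis Plan names the first kind of procedure for a hypothesis of the second kind and gives no success criterion, the rule for declaring success is left open until the data are seen.

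The sub-study equates 230 fmol/punch with about one tablet a week. Its purpose is to judge whether hormone therapy lowers drug exposure enough to matter for PrEP efficacy. A deficit of that size passing as no interaction would be an error on the sub-study's primary objective.

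**Working it through.** **1. Reproduce the planned sample size.** One-sample non-inferiority, normal approximation, one-sided 5%, 80% power:

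n = [SD × (z0.95 + z0.80) / (230 − 100)]² = [350 × (1.645 + 0.842) / 130]² = 44.8, so 45.

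This matches the plan. The figure of 45 therefore belongs to a one-sample test against a fixed reference. The same inputs in a two-sample design with equal groups would need 90 per group.

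**2. Inputs for the comparison that is planned.**

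- MAAB on csHT with perfect adherence: 280 × 70% = 196, and 196 × 25% = 49 (Sample Size and Power).
- MSM comparator: 37 (Preliminary Data).
- SD: 350 is the design value. The +/-694 reported for the 37 MSM is read here as an SD, which is an assumption because the text does not label it.
- t-test level: two-sided 5%, also an assumption, because the Analysis Plan gives none.

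Standard error = √(SD₁²/49 + SD₂²/37):

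- both SDs 350: 76.2
- 350 (MAAB) and 694 (MSM): 124.6
- both SDs 694: 151.2

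**3. If non-significance were the criterion.** The table sets the true deficit at exactly 230 and uses the noncentral t distribution. Degrees of freedom are 84 for equal SDs and about 50 by Welch for the mixed case.

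| SDs (MAAB, MSM) | Chance of a non-significant t-test | Chance of passing the -230 rule |
|---|---|---|
| 350, 350 | 15% | 5% |
| 350, 694 | 56% | 5% |
| 694, 694 | 68% | 5% |

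**4. Where the two criteria disagree on the same data.** The t-test is non-significant when the observed deficit is smaller than t0.975 × SE. Non-inferiority is met when the observed difference exceeds −230 + t0.95 × SE.

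- Both SDs 350: non-significant down to −1.989 × 76.2 = −152. Non-inferiority needs more than −230 + 1.663 × 76.2 = −103. Observed differences from about −152 to −103 are non-significant but fail the rule.
- SDs 350 and 694: the corresponding range is about −250 to −21. An observed deficit larger than the margin itself could be non-significant.

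**5. Power of the -230 rule in the two-sample comparison.** One-sided 5%, 49 against 37, true difference −100, so the distance to the limit is 130:

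- both SDs 350: 52%
- 350 and 694: 27%
- both 694: 21%

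The plan states 80%. The loss at SD 350 comes from the sampling error of the 37 MSM, which the one-sample calculation leaves out. The further loss comes from the larger SD.

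**The case against.** The strongest reply is that the non-inferiority rule is already in the document. The Sample Size and Power text stands just above the Analysis Plan under the same heading, calls this a non-inferiority study, and gives both the margin and the confidence-limit criterion. A two-sample t procedure also produces the interval needed, and the Analysis Plan commits to reporting a 95% interval. On this view a cross-reference is missing and there is no competing decision rule. In addition, Section 9, Statistical Considerations, says that a formal SAP, finalised before database lock, will take precedence.

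Much of this stands. A reader might infer that the plan will treat a non-significant p-value as proof of equivalence. The documents do not say so, and the percentages for non-significance apply only if that were done. A reader might also infer that MSM efficacy estimates would be transferred to transgender women after a non-significant test. Section 7 (Sub-study II Background) makes that transfer conditional on concentrations being not inferior, which supports the non-inferiority reading. Quoting only the 68% case would also overstate the risk, since it gives the comparator's 694 to both groups.

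The gap itself remains. The limit appears only as a power assumption for a one-sample test, and the analysis is two-sample. The 95% interval is not tied to -230. It is also unclear whether the bound would be the one-sided 95% limit of the sample-size text or the lower end of a two-sided 95% interval, which is a one-sided 2.5% test. The text available contains no later rule that settles this.

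**Conclusion.** The point holds as a gap in specification: an equivalence hypothesis and a non-inferiority sample size are paired with a t-test that has no margin or success criterion. A non-significant result could therefore be taken for non-inferiority. If it were, a true deficit at the margin would pass about 15% of the time at the plan's own SD, and 56% to 68% of the time if the comparator's +/-694 is an SD and applies to one or both groups. The intended rate is 5%. These figures assume 49 against 37, normal data and a two-sided 5% t-test.

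This should be fixed for the sub-study. It concerns a non-randomised pharmacology comparison and leaves the randomised iTAB+MI-B versus iTAB comparison untouched.

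**What to change.** In the sub-study Analysis Plan, state that non-inferiority is concluded only if the one-sided 95% lower confidence limit of mean(MAAB) minus mean(MSM) exceeds -230 fmol/punch, which is the lower end of a two-sided 90% interval, and that otherwise the result is inconclusive. The t-test against zero may still be reported, marked as not being the success criterion. In the Section 6 hypothesis, replace 'equivalent' with 'non-inferior'.

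Restate the power to match the two-sample analysis, including the SD assumed for the MSM data.

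The wording costs a few sentences and needs no new data. The real cost is that the rule is stricter than the one-sample design. At a true difference of -100, power is about 52%, or 21% to 27% with the larger SD, so an inconclusive result becomes likely and the sponsor should acknowledge this in advance.
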